2.5.3 Handling of missing values not related to intercurrent event

The primary MMRM model implicitly imputes missing data under MAR assumption.

2.5.3.1 Handling of missing daily pain severity values within a week

The weekly mean of the seven 24-hour average pain severity assessments will be calculated based on the available assessments. If only one measurement is available, the mean will be based on that value. If no measurement is available, the weekly mean VAS score will be missing. The data collected beyond 12 weeks will not be analyzed.

2.5.3.2 Handling of missing weekly mean pain score values

For all analyses, imputation of intermittent missing value of pain severity VAS score before treatment discontinuation will be carried out following a MAR mechanism for all treatment arms.

2.5.4 Supportive analyses

The subgroup analyses will be conducted to assess the consistency of treatment effect across various subgroups described in Section 2.2.1. Subgroup analyses will be conducted using the same model and analysis strategies described in the primary analyses but fitted by category of each of the subgroups. Subgroup variables that are used as fixed effects in the model will be removed from the model statement in the subgroup analysis if applicable. Subgroups will be presented graphically using forest plots. If a subgroup has limited number of subjects, the analyses on this subgroup may fail to converge and not be implemented. Instead, summary statistics for subgroup will be provided.

2.5.4.1 Supplementary estimand

The target population, the primary variable and the summary measure of this estimand are the same as for the primary estimand. The supplementary estimand is defined to estimate the treatment effect of SAF312 versus placebo, regardless of occasional rescue medication, prohibited medications and treatment discontinuations due to any reason.

Novartis	For business use only	Page 18 of 33
SAP		CSAF312B12201

The justification for the supplementary estimand is that they will capture the effect of the study drug when administered in the real world with intercurrent events considered as inherent in the treatment regimen.

Table 2-4	The handling of intercurrent events strategy for supplementary
	estimands

Intercurrent Events	Strategy
Rescue medications for pain relief due to any reason	 All observed data will be used for analysis
	 Missing weekly mean pain score values will be multiple imputed under MAR assumption
Prohibited medications that could confound the primary endpoint (See Table 2-2)	 All observed data will be used for analysis
 Ocular, nasal, inhaled, or systemic corticosteroids 	 Missing weekly mean pain score values will be multiple imputed under MAR
Use of oral or topical ocular antihistamines, mast cell stabilizers	assumption
 Any new use or change in dosing of neuromodulators for any reason, or any 	 All observed data will be used for analysis
use of topical ocular NGF	 Missing weekly mean pain score values will be multiple imputed under MAR assumption
Discontinuation of study treatment due to any reason	 Weekly mean pain score values at or after the week of study treatment discontinuation will be multiple imputed based on J2R assumption for the SAF312 arms and under MAR assumption for the placebo arm

Mixed model covariance matrix will be handled in the same manner as primary estimand.

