12.4.6 Supplementary analysis

A supplementary clinical question of interest is: What is the effect of SAF312 versus placebo on change from baseline in weekly mean pain severity VAS score, regardless of discontinuation from study treatment discontinuations for any reason, and regardless of occasional use of rescue medication or prohibited medications?

The supplementary analysis to the primary analysis will be performed on the FAS population. The supplementary analysis will be performed using all observed data regardless of intercurrent events (a treatment policy strategy). The target population, the primary variable and the summary measure of the supplementary estimand for the supplementary estimand are the same as for the primary estimand. Differently from the primary estimand, this analysis considers all intercurrent events are inherent in the treatment regimen and will not exclude any observed data even when subjects take rescue/prohibited medications or discontinue treatment.

For subjects who use rescue medications for pain relief due to any reason, all observed data will be used for analysis. If not available, missing data will be under the MAR assumption for both SAF312 and placebo arms.

For subjects who take the following prohibited medications:

- Ocular, nasal, inhaled, or systemic corticosteroids
- Use of oral or topical ocular antihistamines, mast cell stabilizers

All observed data will be used for analysis. If not available, missing data on the day(s) +3 days of the IEs will be under the MAR assumption for both SAF312 arms and placebo arm.

For subjects with new use or change in dosing of neuromodulators for any reason or topical ocular NGF, all observed data will be used for analysis. If not available, missing data on the days of IEs will be under the MAR assumption for both SAF312 and placebo arms.

For subjects who discontinue from study treatment due to any reason, retrieved drop-out (RDO) data collected after study treatment discontinuation will be used for analysis. If not available, missing data after treatment discontinuation will be multiply imputed based on Jump to Reference assumption for SAF312 arms and under the MAR assumption for placebo arm.

The supplementary analysis will be performed using MMRM but includes all the observed data and imputed data if appropriate.

Subgroup analysis

Subgroup analyses of the primary endpoints will be outlined in the statistical analysis plan (SAP).

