•	Any new use or change in dosir neuromodulators for any reasor use of topical ocular NGF	ng of • n, or any •	The data starting from the day will be excluded and treated as missing Missing weekly mean pain score values will be handled based on the MAR assumption in MMRM
Discont reasons	inuation of study treatment due t s (e.g. AEs, pandemic)	o any •	The data after study treatment discontinuation will be treated as missing. Weekly mean pain score values at or after the week of study treatment discontinuation will be handled under MAR assumption in MMRM

- The **summary measure** is the treatment difference of the variable means between SAF312 arms and placebo respectively.
 - o SAF312 15 mg/ml vs SAF312 placebo
 - o SAF312 5 mg/ml vs SAF312 placebo

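### The discontinuation row of SAP Table 2-4 imputes weekly pain means from the stopping week onward, observed or not, contrary to the treatment-policy rule in Protocol 12.4.6

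*SAP*

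**What the plan says.** **Protocol 12.4.6.** The supplementary strategy is treatment policy. The analysis "will not exclude any observed data even when subjects take rescue/prohibited medications or discontinue treatment". For subjects who stop treatment, "retrieved drop-out (RDO) data collected after study treatment discontinuation will be used for analysis". Imputation is conditional: "If not available, missing data after treatment discontinuation will be multiply imputed based on Jump to Reference assumption" in the SAF312 arms, and MAR in the placebo arm.

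**SAP 2.5.4.1.** The aim is the same, an effect "regardless of occasional rescue medication, prohibited medications and treatment discontinuations due to any reason". In Table 2-4 the entries for rescue medication, for corticosteroids and antihistamines, and for neuromodulators and NGF each keep all observed data and impute only missing weekly means. The discontinuation row does neither. It reads "Weekly mean pain score values at or after the week of study treatment discontinuation will be multiple imputed based on J2R assumption" for SAF312, with MAR for placebo.

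**SAP section 4** declares no change from the protocol's analyses. **SAP 5.2.2**, headed as the supplementary analysis, has no visible body in the public copy.

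**The concern.** Taken literally, the row imputes every weekly mean from the stopping week on, whether or not the subject recorded pain scores. Retrieved drop-out data, which the protocol says to use, would be discarded. So would a stopping-week mean made up partly or wholly of on-treatment diary days.

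This matters because it is the only planned alternative to the primary handling of discontinuation; Protocol 12.4.5 plans no sensitivity analysis. If the row is followed, the reported result answers a different question from the one both documents pose. J2R in the SAF312 arms would still be a useful check on the primary MAR assumption, but it would be mislabelled.

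**Working it through.** **1. Side-by-side reading**

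| Place | Observed data after stopping | What is imputed |
|---|---|---|
| Protocol 12.4.6 | Used | Only data not available |
| SAP Table 2-4, other entries | Used | Only missing weekly means |
| SAP Table 2-4, discontinuation row | Not mentioned | All weekly means from the stopping week on |
| SAP Table 2-3 (primary estimand), discontinuation row | Removed | All weekly means from the stopping week on |

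The Table 2-4 row shares its timing phrase with Table 2-3. There the phrase follows an explicit removal step, "The data after study treatment discontinuation will be treated as missing", which suits a hypothetical strategy and not treatment policy.

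**2. Does other SAP text restore the condition?**

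- SAP 2.5.3.2 covers "imputation of intermittent missing value of pain severity VAS score before treatment discontinuation", so it stops short of the period at issue.
- SAP 2.5.3.1 makes the stopping week available: "If only one measurement is available, the mean will be based on that value".
- SAP 2.5 defines MAR and J2R but does not say which values they fill.
- SAP 2.7.3 keeps all observed data, but for secondary endpoints only.
- Retrieved drop-out data are not mentioned in the visible SAP.

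**3. The plan's own figure**

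The stated power is 83% (50 per arm, 15 mm, SD 23 mm, two comparisons). A two-sample t calculation at two-sided 0.025 gives 83.6%, so it reproduces. It concerns the primary analysis and does not depend on this row. The same inputs give the standard error of a difference: 23 × √(2/50) = 4.6 mm.

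**4. Illustration of size**

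From the documents: on-drug effect 15 mm. Assumed, because the documents are silent:

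- d: share of subjects who stop, 10% to 30%
- r: share of stoppers with Week 12 data retrieved
- x: their off-drug Week 12 benefit over the imputed value, -5, 7.5 or 15 mm
- stopping week uniform over Weeks 2 to 12, so 1/11 of stoppers stop in Week 12
- on-treatment days in the stopping week uniform over 1 to 7, mean 4
- J2R sets the difference from placebo to zero, and stopping vehicle changes nothing

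Gap (protocol rule minus SAP row as written) = d × [(10/11)·r·x + (1/11)·((1−r)·15 + r·(15·4/7 + x·3/7))]

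Example with d = 20%, r = 1, x = 7.5: 0.2 × [6.82 + (8.57 + 3.21)/11] = 0.2 × 7.89 = 1.58 mm.

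| r | x (mm) | d = 10% | d = 20% | d = 30% |
|---|---|---|---|---|
| 0 | any | 0.14 | 0.27 | 0.41 |
| 0.5 | -5 | -0.13 | -0.26 | -0.39 |
| 0.5 | 7.5 | 0.46 | 0.93 | 1.39 |
| 0.5 | 15 | 0.82 | 1.64 | 2.45 |
| 1 | -5 | -0.40 | -0.79 | -1.19 |
| 1 | 7.5 | 0.79 | 1.58 | 2.37 |
| 1 | 15 | 1.50 | 3.00 | 4.50 |

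At r = 0 the gap is not zero, because the Week 12 mean of subjects who stop in Week 12 is still replaced. In standard errors the table runs from -1.19/4.6 = -0.3 to 4.50/4.6 = 1.0.

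**5. Placebo arm**

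If placebo stoppers with full retrieval improve by 5 mm off vehicle, the gap falls by d × [(10/11)·5 + (1/11)·5·3/7] = d × 4.74, or 0.5 to 1.4 mm for d = 10% to 30%. A 5 mm worsening raises it by the same amount.

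A simulation with outcome-unrelated stopping agreed with the formula to within 0.03 mm. With stopping more likely after worse pain in both arms, it agreed to within 0.10 mm.

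**The case against.** The best defence is that the row is shorthand. Multiple imputation ordinarily fills only missing values. Where the SAP wants observed data removed it says so, as in Table 2-3, and Table 2-4 gives no such instruction. Section 4 declares no departure. New or changed neuromodulator use, or NGF use, requires stopping treatment, and the row for that event keeps all observed data; overwriting would make two rows of one table contradict each other. The body of SAP 5.2.2, where the rule may be set out, cannot be read.

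This makes the shorthand reading plausible, and the intent may well be the protocol's. It does not make the row right. If imputation meant only missing values by default, the qualifier would be redundant in the other entries, yet all of them carry it. The clash with the neuromodulator row equally shows a programmer left with no stated order of precedence. What SAP 5.2.2 says is an open question, but the table should match the protocol either way.

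On size, the objection is sound. Protocol 9.1.1 does not list the pain diary among the minimum data after stopping, and Table 8-1 collects the diary at the end-of-treatment visit, so little may be retrieved. That list is a floor, however: the glossary says subjects who stop treatment agree to the other required assessments. The +4.5 mm corner needs 30% discontinuation, complete retrieval and full persistence of benefit off drug, none of which the documents support.

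**Conclusion.** The concern holds. As worded, the row contradicts Protocol 12.4.6 and the SAP's own statement of the supplementary estimand, and no visible text repairs it. This is a conflict of wording and does not rest on any calculation. It should be corrected, with the caveat that SAP 5.2.2 is not visible and the row may be an abbreviation of the protocol rule.

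The practical effect is not estimable from the documents, in size or in sign. Under the stated assumptions, and before any placebo shift, it lies between about -0.3 and +1.0 standard errors. It is under 0.1 standard error if nothing is retrieved after stopping (0.41/4.6 = 0.09). The primary test and its power are untouched.

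**What to change.** Reword the discontinuation row of SAP Table 2-4 so that every observed weekly mean is kept, including those in and after the week treatment stops, and only missing weekly means are multiply imputed: J2R for the two SAF312 arms, MAR for placebo. Confirm that SAP 5.2.2 and the programming specification follow the same rule. If overwriting is in fact intended, declare it as a departure in SAP section 4 and stop describing the analysis as one that holds whether or not subjects discontinue.

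The cost is one table row, changed before database lock, and one cross-check. No protocol amendment or new data collection is needed.

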2.6 Analysis of the key secondary objective

There is no key secondary objective in the study.

2.7 Analysis of secondary efficacy objective(s)

2.7.1 Secondary endpoints

For secondary endpoints:

- Change from baseline in pain severity Visual Analog Scale (VAS) at Day 7 and Day 14
- Change from baseline to Week 12 in pain frequency VAS
- Change from baseline in OPAS subscale Quality of Life at Week 12
- Change from baseline to Week 12 in ocular surface parameters (corneal staining score, conjunctival staining score, Schirmer score, conjunctival redness score)

Novartis	For business use only	Page 19 of 33
SAP		CSAF312B12201

2.7.2 Statistical hypothesis, model, and method of analysis

No statistical hypothesis test will be performed on the secondary endpoints. Summary statistics (mean, median, 25th percentile, 75th percentile, standard deviation, minimum and maximum, the number of non-missing observations, and 95% confidence interval) by treatment arm will be provided.95% confidence interval will be provided for the difference between the SAF312 arm vs. placebo for pain severity VAS, pain frequency VAS, OPAS subscale Quality of Life and ocular surface parameters.

Where laterality applies, each eye will be summarized separately.

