8.2 Subject demographics/other baseline characteristics

The following information will be collected/documented at Screening/Baseline Visits for each randomized subject:

- Age
- Sex
- Race/Ethnicity
- Ancestry (applicable for Japanese and Chinese only)
- Iris color

Ocular baseline characteristic will include:

- Time since date of the last surgery
- Surgery type (PRK,LASIK, LASEK, RK, SMILE or Cataract)
- Pain Characterization Questionnaire
- Frequency of artificial tear use
- Frequency of rescue medication use
- Corneal fluorescein staining
- Conjunctival lissamine staining
- Conjunctival redness score
- Schirmer score

Baseline values of efficacy parameters:

- Pain Severity VAS
- Pain frequency VAS
- OPAS

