12.4.1 Definition of primary endpoint(s)

The primary endpoint is the change from baseline in weekly mean pain severity VAS at Week 12. The weekly mean pain severity VAS will be calculated as the mean of the daily pain severity VAS from the 7 days of the week. Baseline value will be calculated as the mean of the daily pain severity VAS from the 7 days prior to the first dose.

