2.1.1.2 Baseline and post-Baseline

Baseline (Day 1) is the date of first dose of study treatment. The baseline value for efficacy and safety variables is the last available value collected prior to or at the first date of study treatment. Missing baseline data will not be imputed.

All data collected after the first date of treatment are defined as *post-baseline*. The *study day* for a baseline or post-baseline scheduled or unscheduled visit is defined as:

Study day = (Date of visit) – (Date of first dose of study treatment) + 1;

The study day for a scheduled or unscheduled visit before baseline is defined as

Study day = (Date of visit) – (Date of first dose of study treatment).

2.1.1.3 End of study/end of treatment/unscheduled visit day mapping:

The end of treatment date (date of last exposure from 'Study Treatment' CRF form) is the date of the last study treatment prior to/on the end of study date. The end of study date (from 'Study disposition' CRF) is the date when a subject completes or discontinues the study. For reporting data by visit in outputs, visit window (Section 2.1.1.5) rules will be applied based on study day to allocate assessments to the actual (reported) visit number.

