2.1.1.7 Change from baseline for continuous parameters

Change from baseline will be calculated as:

change from baseline = post-baseline value – baseline value

For summary statistics the raw values (and not imputed values) will be used.

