2.3.2 Demographics and baseline characteristics

Demographics table will include age, sex, race, ethnicity, ancestry, and eye color.

Baseline characteristics table will include: type of prior surgery(PRK,LASIK, LASEK, RK, SMILE or Cataract), time (days) since last surgery, corneal fluorescein staining(sum score), conjunctival lissamine staining(sum score), conjunctival redness score (Temporal and Nasal), schirmer score, Pain Characterization Questionnaire (question 2 only), 7-day average of pain severity VAS score, 7-day average of pain frequency VAS score, 7-day average of artificial tear/gel/lubricant use frequency and 7-day frequency of rescue medication use .

Demographic and baseline characteristics will be summarized for FAS populations by treatment group using frequencies and percentages (for categorical variables) and descriptive statistics of mean, standard deviation, minimum, median and maximum (for continuous variables).

Relevant medical histories and current medical conditions at baseline will be summarized by system organ class, preferred term and treatment group, for ocular and non-ocular histories/conditions, respectively.

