2.7.3 Handling of missing values/censoring/discontinuations

All observed data will be used for analysis and missing data will not be imputed.

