5.2 Statistical models

5.2.1 Primary Analysis

The following MMRM model will be used for the primary estimand and supplementary estimand:

change from baseline in weekly mean pain severity VAS score = intercept + baseline weekly mean pain severity VAS score + treatment + week + treatment*week + baseline weekly mean pain severity VAS score * week + error

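### The 95% CIs for secondary-endpoint differences are not baseline-adjusted, although every baseline is collected; ANCOVA on the same data would be about as narrow or narrower

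*SAP*

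**What the plan says.** SAP 2.7.2 asks for summary statistics by arm and adds that a 95% "confidence interval will be provided for the difference between the SAF312 arm vs. placebo for pain severity VAS, pain frequency VAS", with OPAS Quality of Life and the ocular-surface parameters completing the sentence. No hypothesis test is planned. The section heading announces a model, but none is given. Protocol 12.5 plans the same intervals, except that it does not list the ocular-surface parameters.

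Three other SAP passages show how the interval would be computed:

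- SAP 2.1.1.7 defines change as the post-baseline value minus the baseline value and states: "For summary statistics the raw values (and not imputed values) will be used".
- SAP 2.7.3 states: "All observed data will be used for analysis and missing data will not be imputed".
- SAP 5.2.1 introduces the model containing baseline as a covariate with "The following MMRM model will be used for the primary estimand and supplementary" estimand. The secondary endpoints are not mentioned there.

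The baselines exist. Protocol 8.2 lists pain severity, pain frequency and OPAS under "Baseline values of efficacy parameters", and corneal staining, lissamine staining, redness and Schirmer under ocular baseline characteristics. Protocol Table 8-1 schedules OPAS and the ocular signs at Visit 2.

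The definition of baseline varies. SAP 2.1.1.2 has a general rule: "The baseline value for efficacy and safety variables is the last available value collected prior to or at the first date of study treatment". SAP 2.3.2 instead tabulates the "7-day average of pain severity VAS score, 7-day average of pain frequency VAS score". For the primary endpoint, Protocol 12.4.1 states: "Baseline value will be calculated as the mean of the daily pain severity VAS from the 7 days prior to the first dose".

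**The concern.** With no secondary tests, these intervals are the only planned between-arm inference for pain frequency, OPAS Quality of Life and the ocular-surface scores. The last group carries the secondary objective that SAF312 does not harm the ocular surface, so interval width matters to that judgement. Randomisation is stratified only on baseline pain severity (SAP 1.1), so the design does nothing specific to balance the other baselines.

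A raw difference in mean change fixes the slope of follow-up on baseline at 1. Where the true slope is lower, change scores over-correct for baseline differences and the interval is wider than the data require. The primary analysis avoids this by including the baseline score (SAP 2.5.2). The SAP gives no reason for treating the secondary endpoints differently.

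For pain frequency there is a further ambiguity. The general rule in SAP 2.1.1.2 would make baseline a single diary entry, while SAP 2.3.2 points to a 7-day mean.

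**Working it through.** **Inputs from the documents.** 50 per arm, allocated 1:1:1 (SAP 1.1 and 3). SD of change 23 mm for weekly mean pain severity (SAP 3). The documents state no figure for the secondary intervals.

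**Reproducing the plan's own figure.** For a 15 mm difference, SD 23 mm, 50 per arm and two-sided alpha 0.05/2 = 0.025, the two-sample t calculation with 98 df gives 83.6% power. With the Dunnett critical value of 2.234 on 147 df it is 84.7%. The SAP says approximately 83%, so its figure reproduces. The 23 mm is used below for illustration only.

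**Assumed inputs.** The baseline/follow-up correlation ρ and the SD ratio k = follow-up SD / baseline SD are not in the documents, so ranges are shown.

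**Formula.** In units of the baseline variance:

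- variance of change = 1 + k² − 2ρk
- ANCOVA residual variance = k²(1 − ρ²)
- the first minus the second = (1 − ρk)², which is never negative and is zero only when ρk = 1

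The CI width ratio is the square root of R = k²(1 − ρ²)/(1 + k² − 2ρk). The number per arm an unadjusted comparison would need for the same width is 50/R. Example at k = 1, ρ = 0.5: R = 0.75/1 = 0.75, width ratio 0.866, 50/0.75 = 67.

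| k | ρ = 0.3 | ρ = 0.5 | ρ = 0.7 |
|---|---|---|---|
| 0.8 | R 0.502, 29% narrower | R 0.571, 24% | R 0.628, 21% |
| 1.0 | R 0.650, 19% (n 77) | R 0.750, 13% (n 67) | R 0.850, 8% (n 59) |
| 1.3 | R 0.805, 10% (n 62) | R 0.912, 4.5% (n 55) | R 0.991, 0.5% (n 50) |
| 1.6 | R 0.896, 5% (n 56) | R 0.980, 1% (n 51) | R 0.989, 0.5% (n 51) |

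**In millimetres.** The unadjusted half-width is t(0.975, 98) × 23 × √(2/50) = 9.13 mm. With equal SDs the ANCOVA residual SD is 23 × √((1 + ρ)/2), and the half-width is t(0.975, 97) × that SD × √(2/50) × √(1 + 1/96). This gives 7.40, 7.95 and 8.46 mm at ρ = 0.3, 0.5 and 0.7.

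**Finite-sample cost.** With normal data, three arms of 50 and pooled residual variance, simulated mean width ratios at k = 1 were 0.809, 0.868 and 0.926. In the least favourable case, ρk = 1, the mean ratio was 1.003. A two-arm fit gave 1.005, with a 97.5th percentile of about 1.03. Coverage was close to 95% for both methods throughout. No subject is lost, because a change score already requires a baseline.

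**Bounded scores.** For simulated skewed, floor-heavy grades on 0–8 and 0–5 scales, ANCOVA narrowed the interval by 10–21% with 94–96% coverage.

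**Pain severity.** The 30 mm entry cut-off truncates the baseline and raises k. Assume a mean of 45, 55 or 60 mm and SD 20 mm before the cut, equal SDs before the cut, and ρ from 0.3 to 0.7. Then k becomes 1.12–1.34 and the narrowing is 4.4–14.1%.

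**The case against.** The strongest counter-argument is that the SAP never says unadjusted. In SAP 2.1.1.7 raw is contrasted with imputed, not with covariate-adjusted. SAP 2.7.3 concerns missing data only, and SAP 5.2.1 does not say that its model is used nowhere else. That is correct: the reading is an inference. It is still the natural one, because the interval is listed beside raw summary statistics with no model or covariate named. If something else was intended, SAP 2.7.2 needs the same edit to say so.

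Second, this is a choice and not an error. There is no key secondary objective and no secondary test, the unadjusted difference is unbiased, and coverage is nominal. All of that stands and limits the weight of the point.

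Third, the size rests on assumed correlations and SD ratios, and the gain may be close to nil. That stands too. It applies most to Day 7 and Day 14 pain severity, which read as single-day values and probably vary more than a 7-day mean. If follow-up SD before the entry cut is 1.2 or 1.4 times baseline, the 4.4–14.1% falls to 0.9–9.0% or 0.0–5.7%. The primary MMRM also already reports adjusted Week 1 and Week 2 differences, though on weekly means under the hypothetical strategy.

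Fourth, a linear model is approximate for short grading scales. An unadjusted mean difference also treats grades as numbers, and the simulation of such scores showed no loss of coverage.

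Fifth, SAP 2.1.1.6 says pain frequency is handled like pain severity, by weekly averaging, which already favours a 7-day baseline. That supports the proposed definition but does not remove the conflict with SAP 2.1.1.2.

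**Conclusion.** The point holds, as an improvement to consider. Read as a whole, the SAP plans unadjusted differences in mean change for the secondary endpoints, while the covariate that would sharpen them is already collected. Over the assumed grid (ρ from 0.3 to 0.7, k from 0.8 to 1.6) the intervals would narrow by between 0.5% and 29%. The least favourable case is a mean widening of 0.3–0.5%, rarely above 3% in a single trial. Adjustment would also take chance baseline imbalance out of the estimates.

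The primary result, type I error and sample size are unaffected. Confidence in the size is moderate, because neither ρ nor k can be taken from the documents.

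**What to change.** In SAP 2.7.2, obtain each SAF312–placebo difference and its 95% CI from an ANCOVA of change from baseline at the stated time point, with treatment and the endpoint's own baseline as covariates. Use observed data as in SAP 2.7.3, and fit each eye separately where laterality applies. Name the 7-day mean before first dose as the baseline for both pain severity and pain frequency VAS, and make SAP 2.1.1.2 agree. Keep the raw summaries as descriptive tables and add no hypothesis tests. State that the linear model is an approximation for bounded grades such as lissamine (0–8) and redness (0–5).

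The cost is a few sentences of SAP text and about 14 simple fits. Four are at subject level: Day 7 and Day 14 pain severity, pain frequency and OPAS Quality of Life. Ten are per eye: corneal staining, lissamine, Schirmer, temporal redness and nasal redness, 5 × 2 eyes. Data collection and sample size do not change.
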